6.3. Appendix 3 Data Derivations Rule

6.3.1. Attributing events to vaccine doses

If an event starts on the same day as a study dose, the relative dose will be derived from the additional information provided in the eCRF using the contents of the flag indicating if the event occurred before or after study dose. If 'after study dose' is selected, the relative dose for the event will be the one administered on the start day of the event. If 'before study dose' is selected, the event will not be attributed to the study vaccination.

6.3.2. Handling of missing data

6.3.2.1. Dates

When partially completed dates (i.e., dates missing a day and/or month) are used in calculations, the following standard rules will be applied:

- A missing day will be replaced by 15
- A missing day and month will be replaced by June 30th.

The following exceptions apply:

- Adverse events start dates with missing day:
 - If the month is not the same as the vaccine dose, then the imputed start date will be the 1st of the month.
 - If the event starts in the same month as the vaccine dose, the flag indicating if the event occurred before or after vaccination (AE.AESTRTPT) will be used to complete the date. If ‘after vaccination’ is selected, the imputed start date will match the vaccine dose given during that month. If ‘before vaccination’ is selected, the imputed date will be one day before the vaccine dose given during that month.
- Adverse events start dates with missing day and month:
 - If the year is not the same as the vaccine dose, then the imputed start date will be the 1st of January.
 - If the event starts in the same year as the vaccine dose, the flag indicating if the event occurred before or after vaccination (AE.AESTRTPT) will be used to complete the date. If ‘after vaccination’ is selected, the imputed start date will match the vaccine dose given during that year. If ‘before vaccination’ is selected, the imputed date will be one day before the vaccine dose given during that year.
- Adverse event end dates with missing day: the imputed end date will be the last day of the month or the study conclusion date whichever comes first.
- Adverse event end dates with missing day and month: the imputed end date will be the last day of the year (31st of December) or the study conclusion date whichever comes first.

All incomplete concomitant medication/vaccination start/end dates will follow the rules above.

6.3.2.2. Laboratory data

Any missing or non-evaluable immunogenicity measurement will not be replaced. The descriptive analysis performed for each assay at each timepoint will exclude participants with a missing or non-evaluable measurement. This is applicable to the standard way of computing geometric mean titers/concentrations (GMTs/GMCs).

6.3.2.3. Daily recording of solicited events

For the analysis of solicited events, the daily assessment from the investigator (either to correct the participant entry or to replace a missing participant entry) will take precedence over the participant's entry only when the investigator assessment is done up to 36 hours after 23h59 of the specified day.

In case of missing/incomplete dates or times of either participant entries or investigator assessments, rules have been put in place to decide whether or not to use the investigator assessment. These derivation rules will be part of the ADaM specifications.

The following table shows how participants contribute to each category for a specific solicited event over the Day X to Day Y post-dose period:

Solicited event category	Participants included in the calculation of the numerator
Any	All participants with at least one occurrence of the adverse event at grade 1, grade 2, or grade 3 between Day X and Day Y
Grade 3	All participants with at least one occurrence of the adverse event at grade 3 between Day X and Day Y

6.3.2.4. Unsolicited adverse events

Unsolicited adverse event summaries are including serious adverse events unless specified otherwise.

Missing severity, relationship with study vaccine, and outcome of unsolicited adverse events will not be replaced and will appear as 'UNKNOWN' when displayed in a statistical output.

6.3.3. Data derivation

6.3.3.1. Age at vaccination in years and age category

Age will be calculated as the number of years between the year of birth and the year of vaccination. The age group will be derived based on derived age.

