5.1. Inclusion criteria

Participants are eligible to be included in the study only if all of the following criteria apply:

- Participants and/or participant's parent(s)/LAR who, in the opinion of the investigator, can and will comply with the requirements of the protocol (e.g., completion of the eDiary, attend study site visits, ability to access and utilize a phone or other electronic communications). INC#1

Note: for participants in case of physical incapacity that would preclude the self-completion of the eDiary, either (i) site staff can assist the participant (for activities performed during site visits) (ii) or the participant may assign a caregiver to assist him/her with this activity (for activities performed at home). However, at no

time will the site staff or caregiver evaluate the participant's health status while completing eDiaries or make decisions on behalf of the participant.

- Written or witnessed informed consent obtained from the participant/participant's parent(s)/LAR(s) (participant must be able to understand the informed consent) prior to performance of any study-specific procedure. INC#2

Written informed assent obtained from the participant (participant must be able to understand the informed assent) if he/she is less than the legal age* prior to performance of any study-specific procedure.

**The legal age is determined according to local regulations in each participating country. In case the legal age is achieved during the conduct of the study, an additional written informed consent from the participant should be obtained at the time of the legal age.*

5.1.1. Specific inclusion criteria for all participants in Cohort 1 and Cohort 3

- A male or female participant 18-49 YOA at the time of the study intervention administration. INC#3
- Participants should be diagnosed with at least 1 of the following medical conditions if considered medically stable* by the investigator: INC#4

**A stable condition is defined as a disease not requiring significant change (based on the investigator's opinion) in therapy or worsening during the 3 months before enrollment.*

- Chronic cardiopulmonary disease resulting in activity restricting symptoms or use of long-term medication:
 - Chronic obstructive pulmonary disease (COPD)
 - Global Initiative for Chronic Obstructive Lung Disease (GOLD) Grade 2-4
 - Asthma
 - Patient on Maintenance and Reliever Therapy (MART) OR with at least one rescue treatment per week (excluding exercise asthma)

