 - Cystic fibrosis
 - Other chronic respiratory diseases: lung fibrosis, restrictive lung disease, interstitial lung disease, emphysema or bronchiectasis
 - Chronic heart failure:
 - A minimum of class II symptoms according to New York Heart Association classification of heart failure
 - Pre-existing CAD (CAD not otherwise specified)

- Physician diagnosis of CAD based on electrocardiogram, exercise stress test, nuclear stress test, cardiac computed tomography scan or cardiac angiogram (more than the presence of hypercholesterolemia)
 - Cardiac arrhythmia
 - Patient diagnosed with a cardiac arrhythmia that require medical support either pharmacologically or with a medical device
- Diabetes mellitus: types 1 or 2 with active treatment for the past 6 months
- Other diseases at increased risk for RSV disease
 - Chronic kidney disease
 - G2-G3 disease (Glomerular Filtration Rate between 30 and 90 ml/min/1.73 m²)
 - Chronic moderate to severe liver disease
 - Neurologic or neuromuscular conditions (for specific exclusion criteria, see Section 5.2.1)
- Female participants of non-childbearing potential may be enrolled in the study. Nonchildbearing potential is defined as premenarche, hysterectomy, bilateral oophorectomy, bilateral salpingectomy or post-menopause. INC#5
- Female participants of childbearing potential may be enrolled in the study, if the participant:
 - has practiced adequate contraception from 1 month prior to study intervention administration, and
 - has a negative pregnancy test on the day of study prior to intervention administration, and
 - has agreed to continue adequate contraception for at least 1 month after completion of the study intervention administration. INC#6

Refer to Section 10.4.1 for definitions of woman of childbearing potential and non-childbearing potential, and Section 10.4.2 on adequate contraception.

5.1.2. Specific inclusion criteria for all participants in Cohort 2

- A male or female participant ≥ 60 YOA at the time of the study intervention administration. INC#7
- Participants with chronic stable medical conditions with or without specific treatment, such as diabetes, hypertension or cardiac disease are allowed to participate in this study if considered medically stable* by the investigator. INC#8

**A stable condition is defined as disease not requiring significant change (based on the Investigator's opinion) in therapy or worsening disease during the 3 months before enrollment.*

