4.6. Other Analyses

4.6.1. Subgroup analyses

4.6.1.1. Immunogenicity analysis by age at vaccination

As exploratory analysis, the descriptive within group immunogenicity analysis (humoral results) points a, b, c, e (except the graphical displays) and g described in Section 4.3.2.2.2 will also be generated by age at vaccination: 18-49 YOA, 60-69 YOA and ≥ 70 YOA.

CCI

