6.1.2. Demographic and Baseline Characteristics

Demographic and baseline characteristics (age at vaccination in years, sex, race, ethnicity, country, vital signs, Body Mass Index (BMI) and smoking status) will be summarized by group using descriptive statistics. This analysis will be based on the ES, PPS and on the CCI subset of the ES and PPS for all the parameters except vital signs. The vital signs will be summarized based on the ES. If the summary of demographic characteristics for public disclosure meets the criteria for de-identification, as described in the relevant procedural document, a de-identified version will be produced.

The following age categories will be considered in the analysis: 18-49 YOA, 60-69 YOA, ≥ 70 YOA and ≥ 80 YOA. In addition, for web posting purposes: 18-64 YOA, 65-84 YOA and ≥ 85 YOA.

The number and percentages of participants with medical history classified by the MedDRA Primary SOC, HLT and PTs will be tabulated by group for the ES. The same tabulation will be done for the ongoing baseline chronic diseases of interest.

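### SAP 6.3.3.1 derives age from calendar years, so an eligible 49-year-old can be derived as 50 and fall outside every analysis age category, and some 69-year-olds are counted as 70 or over; only descriptive tables are affected

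*SAP*

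**What the plan says.** **Derivation.** SAP 6.3.3.1: "Age will be calculated as the number of years between the year of birth and the year of vaccination". It continues: "The age group will be derived based on derived age". Protocol 8.1.1 gives year of birth as the only birth item it names among the demographic data.

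**Eligibility.** Protocol 5.1.1, for Cohorts 1 and 3: "A male or female participant 18-49 YOA at the time of the study intervention administration". Protocol 5.1.2 sets the Cohort 2 minimum in the same terms: "60 YOA at the time of the study intervention administration. INC#7".

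**Where the categories are used.**
- SAP 6.1.2, demography: "The following age categories will be considered in the analysis: 18-49 YOA, 60-69 YOA", followed by 70 and over and 80 and over. A second list is for disclosure only: "In addition, for web posting purposes: 18-64 YOA, 65-84 YOA", followed by 85 and over.
- SAP 4.6.1.1, immunogenicity: results are "generated by age at vaccination: 18-49 YOA, 60-69 YOA", followed by 70 and over. This display is introduced as "As exploratory analysis, the descriptive within group immunogenicity analysis".

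Neither document says what to do with an eligible participant whose derived age is 50.

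**The concern.** Eligibility and analysis use two different ages. The inclusion criteria use age on the day of vaccination; the SAP uses the difference between two calendar years. The two disagree for anyone vaccinated before their birthday in that year, and always in the same direction, so the error does not average out.

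At the upper edge of the younger group the disagreement lands in a gap, because apart from the web-posting band no category covers 50 to 59. Followed literally, the rule leaves some properly enrolled participants without a row in the demography age categories and in the immunogenicity display by age. The 18-49 row then need not match the group total. The age summary could show a maximum of 50 in a group defined as 18-49, which looks like an eligibility deviation when none occurred. In Cohort 2 nobody is lost, but some participants move from 60-69 to 70 and over.

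**Working it through.** The plan states no figure to reproduce here. The check is of the rule itself, followed by an illustration of size.

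**1. Behaviour of the rule.** Derived age = year of vaccination − year of birth. Completed age is the same, less 1 if the birthday is still to come that year. Derived minus completed age is therefore 0 or +1. A run of 300,000 simulated pairs of birth and vaccination dates gave only these two values.

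**2. Worked dates (vaccination on 1 June 2024).**

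| Born | Completed age | Derived age | Category from derived age |
|---|---|---|---|
| 15 Nov 1974 | 49 | 50 | none (18-64 web band only) |
| 15 Nov 1954 | 69 | 70 | 70 and over |
| 15 Nov 1944 | 79 | 80 | 80 and over |

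Across the simulated eligible participants, those aged 18-49 had derived ages from 18 to 50, and those aged 60 and over never fell below 60. The gap is therefore at 50 only. The other boundaries give misclassification, not loss.

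**3. Which displays.** The demography categories cover Cohorts 1, 2 and 3. Immunogenicity is assessed in Part A only (Protocol 8.2, SAP 4.3.2.2), so the display in SAP 4.6.1.1 involves Cohorts 1 and 2 only.

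**4. Illustrative size.**

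From the documents: 425 in each of Cohorts 1 and 2, 600 in Cohort 3, and 361 evaluable per Part A cohort. Under the enrolment rule, 60-69 makes up 40% to 70% of Cohort 2 (40% plus up to the free 30%).

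Assumed, not in the documents: birthdays spread evenly over the year; ages uniform over the 32 single years 18-49 and the 10 single years 60-69; everyone vaccinated on one date in a 366-day year.

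P(+1) = 1 − fraction of the year elapsed. For 1 July, 1 − 182/366 = 0.503.

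- Cohort 1 derived as 50: 425 × 0.503 / 32 = 6.7. On 361 evaluable: 361 × 0.503 / 32 = 5.7.
- Cohort 3 derived as 50 (demography only): 600 × 0.503 / 32 = 9.4.
- Cohort 2 moved from 60-69 to 70 and over: 425 × 0.40 × 0.503 / 10 = 8.5, up to 425 × 0.70 × 0.503 / 10 = 15.0.

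**5. Sensitivity to the vaccination date, same age assumptions.**

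| Date | P(+1) | Cohort 1 derived as 50 | Cohort 2 moved up |
|---|---|---|---|
| 15 January | 0.962 | 12.8 | 16.3-28.6 |
| 1 July | 0.503 | 6.7 | 8.5-15.0 |
| 15 December | 0.046 | 0.6 | 0.8-1.4 |

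A different age mix would move these further: the count derived as 50 is proportional to the share of the cohort aged 49, which the documents do not give.

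**The case against.** **The rule follows from the data.** If only year of birth is held, a calendar-year difference is the only age that can be computed, and the SAP states it openly. This stands as an explanation and is why the fix asks for no new data. It does not close the gap at 50, because enrolled cohort is known for everyone and settles the 18-49 category without a birth date.

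**Little is lost.** The display in SAP 4.6.1.1 is exploratory and descriptive. Its 18-49 row is meant to hold the same people as the RSV-A-AIR group, whose results are already reported by group. No hypothesis or success criterion uses the split at 70. All of this stands, and it is why the point is minor.

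**A stronger reading.** SAP 3 bases the Exposed Set and Per-Protocol Set groups on age and medical condition without saying which age. A reader might infer that someone derived as 50 drops out of the RSV-A-AIR group, and so out of the non-inferiority comparison or the safety tables. The documents do not support that. Protocol 4.1 labels Cohorts 1 and 3 the RSV-A-AIR Group and Cohort 2 the RSV-OA Group. SAP 4.2.2 names the primary comparison by cohort, and SAP 5 equates combined Cohorts 1 and 3 with the RSV-A-AIR group. Nor would a derived age of 50 trigger elimination code 2010, which covers deviations from the inclusion and exclusion criteria; those use age at vaccination.

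**Conclusion.** The point holds and is minor. The category gap follows from the text alone and needs no assumption beyond reading SAP 6.3.3.1 as a difference of calendar years. It is a stated rule that gives the wrong category, or none, for some eligible participants, and nothing else in the documents corrects it.

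Its reach is the descriptive demography categories and the exploratory immunogenicity display by age. The conclusion that the primary and safety analyses are untouched rests on groups following enrolled cohort, which the documents indicate but SAP 3 does not state.

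The number affected cannot be determined, because neither the age mix nor the vaccination dates are given. The counts above show only the order of magnitude under the stated assumptions; they are not bounds.

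**What to change.** 1. **SAP 6.3.3.1, younger group.** Assign every participant enrolled as eligible in Cohorts 1 and 3 to the 18-49 category by enrolled cohort, whatever the derived age.
2. **SAP 6.3.3.1, Cohort 2.** For 60-69 versus 70 and over, use the age category under which the participant was enrolled (Protocol 6.3.3) if it rests on completed age; the documents do not say whether it does. Otherwise keep the calendar-year derivation.
3. **Footnote, in all cases.** On every age display, state that age is vaccination year minus birth year and may exceed completed age by one year, so that a value of 50 in the 18-49 group is not an eligibility deviation. This is needed even after step 1, because the continuous derived age can still show 50. It also covers the cut-points at 65, 80 and 85.
4. **SAP 3, clarification of documented intent.** State that the Exposed Set and Per-Protocol Set groups follow enrolled cohort (Cohorts 1 and 3 = RSV-A-AIR, Cohort 2 = RSV-OA), so that derived age cannot remove anyone from a group.

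The cost is a few sentences of SAP wording and one standard footnote. No new eCRF field and no retrieval of birth dates is needed.

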6.3.3.2. Weight

Weight will be presented in kilograms. Weights reported in pounds will be converted as follows:

$$\text{Weight in kilograms} = \text{Weight in pounds} / 2.2$$

6.3.3.3. Height

Height will be presented in centimeters. Heights reported in feet and inches will be converted as follows:

$$\text{Height in centimeters} = \text{Height in inches} \times 2.54$$

6.3.3.4. Body mass index (BMI)

BMI will be calculated as follows:

$$\text{BMI} = (\text{Weight in kilograms}) / (\text{Height in meters})^2$$

6.3.3.5. Temperature

Temperatures will be presented in degrees Celsius (°C). Temperatures reported in degrees Fahrenheit (°F) will be converted as follows:

$$\text{Temperature (Celsius)} = ((\text{Temperature (Fahrenheit)} - 32) \times 5)/9$$

6.3.3.6. Numerical serology results

Numerical serology results will be derived from the content of IS.ISORRES in the SDTM dataset. For assays with a specific cut-off, the following derivation rules apply:

IS.ISORRES	Derived value
“NEG”, “-”, or “(−)”	cut-off/2
“POS”, “+”, or “(+)”	cut-off
“< value” and value is \leq assay cut-off	cut-off/2
“< value” and value is $>$ assay cut-off	value
“> value” and value is $<$ assay cut-off	cut-off/2
“> value” and value is \geq assay cut-off	value
“value” and value is $<$ cut-off	cut-off/2
“value” and value is \geq cut-off and value is \leq ULOQ	value
“value” and value is $>$ ULOQ	ULOQ
All other cases	missing

6.3.3.7. Geometric mean titers (GMTs) and concentrations (GMCs)

GMT or GMC calculations are performed by taking the inverse logarithm of the mean of the log titre or concentration transformations. Non quantifiable neutralizing titres or concentrations will be converted as described in Section 6.3.3.6 for the purpose of GMT/GMC calculation. Cut-off values are defined by the laboratory before the analysis.

6.3.3.8. Onset day

The onset day for an event (e.g. AE, concomitant medication/vaccination) is the number of days between the study dose and the start date of the event. This is 1 for an event occurring on the same day as a study dose (and reported as starting after study dose).

6.3.3.9. Duration of events

The duration of an event with a start and end date will be the difference between the start and end date plus one day, i.e., an event that starts on 03MAR2018 and ends on 12MAR2018 has a duration of 10 days.

For solicited administration site and systemic events:

- The duration of a solicited AE with at least one day Grade > 0 is defined as End date – Start date + 1, with Start date defined as the first day with the symptom and End date defined as the last day with the symptom in or beyond the solicited period, considering the investigator assessment within 36h and the intensity of the symptom.
- A missing start date will be imputed with the vaccination date.
- The number of days with grade 3 solicited symptom will be defined considering each day with a known grading=3, irrespective of whether the days are consecutive.

To account for missing eDiary data as of day 5 onwards (due to non-activation of the eDiary alerts for participants from day 5 onwards in the vendor system), a sensitivity analysis will be performed using the below definition of duration:

- The duration of a solicited AE with at least one day Grade > 0 is defined as End date – Start date + 1, with Start date defined as the first day with the symptom and End date defined as the day before the first occurrence of the symptom (in or beyond the solicited period) equals ‘N’ with no days having occurrence ‘Y’ afterwards.
- A missing start date will be imputed with the vaccination date.
- If a solicited event is still not reported as ‘N’ at day 30, the end date will be considered equal to vaccination date + 29 days.

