- If any individual other than the participant/participant's parent(s)/LAR(s) is making entries in the eDiary, their identity must be documented in the participant's source record.
- The completed eDiary will be collected and verified during discussions with the participant/participant's caregiver(s) on Visit 2.
- All solicited events that occur during the four days following administration of the dose of the study intervention (Day 1 to Day 4) must be recorded into the eDiary, irrespective of intensity. An automatic reminder to complete the eDiary will be sent to the participants during this time frame. Daily eDiary compliance will be checked by the investigator or delegate on the eDiary portal. In case of non-compliance, the investigator should contact the participant to remind the importance of daily entries. All other AEs occurring within this time frame should be recorded into the appropriate section of the eCRF, irrespective of their intensity or whether or not they are considered related to the study intervention.
- After review and verbal discussion of the eDiary entries with the participant/participant's parent(s)/LAR(s), if there are clear eDiary errors the investigator will complete his/her own assessment in the relevant sections of the eCRF.
- Note: eDiary may be completed by a minor participant under the supervision of the participant's parent(s)/LAR(s) provided the minor is capable of assessing and reporting the information to be recorded on eDiary. The ultimate accountability for completion of the eDiary remains with the participant's parent(s)/LAR(s). The investigator should discuss this accountability with the participant's parent(s)/LAR(s).
- The investigator or delegate should verify the reported information during a discussion with the minor participant preferably in the presence of their parent(s)/LAR(s).

- Return of the eDiary device is not applicable if the participant has BYOD but verification of the recorded data should always take place.
- Any unreturned eDiary will be sought from the participant/participant's parent(s)/LAR(s) through telephone call(s) or any other convenient procedure.
- Data on solicited events reported in the eDiary will be electronically transferred to the eDiary vendor, where it can be monitored by appropriately qualified site staff and sponsor staff through a web-based portal.
- Refer to the eDiary Manual for more information regarding the use of eDiary.

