- For fever, the number and percentage of participants reporting fever by half degree (°C) cumulative increments during the 4-day follow-up period after vaccination will be tabulated.
- The percentage of participants with each solicited administration site event and solicited systemic event (any grade and Grade 3) during the 4-day follow-up period after vaccination will be represented graphically.
- The duration in days of each individual solicited event will be tabulated using descriptive statistics (mean, min, Q1, median, Q3, maximum). The same computations will be done for the number of days with Grade 3 solicited events. The duration will be calculated for both definitions in Section [6.3.3.9](#) and the outputs will be tabulated for all participants and for the participants from Cohort 3 enrolled as of 8August24, as from then the eDiary alerts for participants from Day 5 onwards were activated in the vendor system.
- The number and percentage of participants with any unsolicited AEs during the 30-day follow-up period (i.e., the day of vaccination and 29 subsequent days) with its exact 95% CI will be tabulated by group and by MedDRA Primary System Organ Class (SOC), High Level Term (HLT) and Preferred Term (PT). Similar tabulation will be done for Grade 3 unsolicited AEs, for any causally related unsolicited AEs,

for Grade 3 causally related unsolicited AEs and for unsolicited AEs resulting in a medically attended visit. The analyses of unsolicited AEs will include SAEs and AESIs (i.e. pIMDs and AF).

- The number and percentage of participants with any non-serious unsolicited AEs during the 30-day follow-up period (i.e., the day of vaccination and 29 subsequent days) with its exact 95% CI will be tabulated by group and by MedDRA Primary SOC, HLT and PT. Similar tabulation will be done for Grade 3 non-serious unsolicited AEs, for any causally related non-serious unsolicited AEs, for Grade 3 causally related non-serious unsolicited AEs and for non-serious unsolicited AEs resulting in a medically attended visit.
- The number and percentage of participants with any unsolicited AEs reported within 30 minutes following vaccination with its exact 95% CI will be tabulated by group and by MedDRA Primary SOC, HLT and PT. Similar tabulation will be done for Grade 3 unsolicited AEs reported within 30 minutes following vaccination.

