4.7. Interim Analyses

4.7.1. Sequence of analysis

The analyses will be performed stepwise:

- **Day 31 (Part A):** A first analysis will be performed on all immunogenicity, reactogenicity and safety data available and as clean as possible, when data for at least primary and secondary endpoints up to Visit 2 (Day 31) are available for all participants in Part A. This analysis will be considered as final for the primary endpoints.
- **Month 6 (Part A):** If required, a safety analysis can be performed when safety data up to Month 6 are available and as clean as possible, for all participants in Part A.
- **Day 31 (Part B):** If required, a safety analysis can be performed when safety data up to Visit 2 (Day 31) are available and as clean as possible, for all participants in Part B. This analysis may be combined with Month 6 safety analysis for Part A.
- **Month 6 (Part A):** If required an immunogenicity analysis can be performed when all data for secondary endpoints up to study conclusion (Visit 3, Month 6) are available and as clean as possible, for all participants in Part A.

- An **EOS** analysis will be performed when all immunogenicity and safety data up to study conclusion (Visit 3/Contact, Month 6) will be available for all participants in Part A and Part B.
- If the data of different analyses become available around the same timepoint, these analyses can be combined into one analysis.

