5. SAMPLE SIZE DETERMINATION

The target sample size for the study is approximately 850 participants: 425 participants in Cohort 1 (RSV-A-AIR [18-49 YOA group]) and 425 participants in Cohort 2 (RSV-OA [≥ 60 YOA group]), to obtain at least 722 evaluable participants (361 participants in the RSV-A-AIR [18-49 YOA] cohort and 361 participants in the RSV-OA [≥ 60 YOA] cohort) for the evaluation of the primary objectives, assuming that approximately 15% of the enrolled participants will not be evaluable.

Participants who withdraw from the study will not be replaced.

The power to demonstrate the primary NI objectives following the hierarchical testing procedure described in Section 2.1 is presented in [Table 6](#).

Table 6 Power for primary objectives of non-inferiority of the humoral immune response after RSVPreF3 OA vaccine between the RSV-A-AIR (18-49 YOA) Cohort 1 to RSV-OA (≥ 60 YOA) Cohort 2 for 361 evaluable participants per group

Objective	Standard deviation (SD) of log10 titers / SRR (%)	Non-inferiority margin	Type II Error	Power ¹
NI for RSV-A strain				
GMT RSV-A	SD=0.45	1.5	0.05	99.95%
SRR RSV-A	SRR=81.6% ²	10%	6.92	93.08%
Global power for RSV-A strain				93%
NI for RSV-B strain				
GMT RSV-B	SD=0.45	1.5	0.05	99.95%
SRR RSV-B	SRR=78.7% ²	10%	9.56	90.44%
If non-inferiority is demonstrated for RSV-A, global power for RSV-B strain				90%

NI=Non-inferiority; SRR=Seroresponse rate; GMT=Geometric mean titer; RSV=Respiratory syncytial virus

¹Pass 2019 1-sided alpha=2.5% for each endpoint (GMT ratio and SRR difference), two-Sample T-Tests for Non-Inferiority assuming equal variance for group GMT ratios and Miettinen and Nurminen for Non-Inferiority tests for group SRR difference, Non-inferiority limit=0.176 (=log10(1.5)) for group GMT ratios

²Reference from RSV OA=ADJ-006

For the evaluation of reactogenicity and safety, the sample size of 1025 participants in combined Cohorts 1 and 3 (RSV-A-AIR group) has 64% and 87% probability of observing at least one vaccinated participant with AE if the true AE incidence rate is 0.1% and 0.2% respectively. This probability increases to at least 95% for true AE incidence rates $\geq 0.3\%$.

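### Does the sensitivity definition of solicited-event duration need a count of events closed at Day 30, or a further split by eDiary alert status?

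*SAP*

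**What the plan says.** SAP 6.3.3.9 gives two durations for a solicited event, both computed as end minus start plus one day.

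- Main definition: "End date defined as the last day with the symptom in or beyond the solicited period".
- Second definition, introduced because of the missing data from Day 5: "a sensitivity analysis will be performed using the below definition of duration". The event ends the day before the first recorded 'no' that has no later 'yes'. If there is still no 'no' at Day 30, "the end date will be considered equal to vaccination date + 29 days".

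SAP 4.3.2.1 summarises both by group with mean, minimum, quartiles, median and maximum, and "the outputs will be tabulated for all participants and for the participants from Cohort 3 enrolled as of 8August24". SAP 6.2.2 adds diary compliance by group and symptom, from Day 1 and from Day 5, for the same two populations.

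Late correction is limited. Protocol 10.3.5.1 states "The completed eDiary will be collected and verified during discussions with the" participant or caregiver at Visit 2, but under SAP 6.3.2.3 an investigator's entry overrides or replaces the participant's "only when the investigator assessment is done up to 36 hours after 23h59 of the specified day".

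Groups follow age and medical condition (SAP 3), and SAP 5 refers to a "sample size of 1025 participants in combined Cohorts 1 and 3 (RSV-A-AIR group"). For Part A alone, SAP 4.7.1 says: "A first analysis will be performed on all immunogenicity, reactogenicity and safety data available and as clean as possible" once the Day 31 data are in.

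**The concern.** For an event still present on Day 4 with no later entry, the truth is unknown. The main definition assumes that it ended on Day 4, the sensitivity definition that it lasted to Day 30. The first tends to be too short and the second too long. The Visit 2 review comes at least 30 days after vaccination, far outside the 36-hour window, so it cannot close these events.

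Two things then seem to be missing. First, nothing planned states how many events were ended by the Day 30 rule, so a reader who sees two different means cannot tell whether a few events or many caused the gap. Second, pooled RSV-A-AIR tables combine participants with and without Day 5 alerts and sit beside an RSV-OA column for which no alerts-on table exists. A difference in mean duration between the groups could then reflect alert status alone. At stake is the reading of a reactogenicity summary.

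**Working it through.** **The plan's own figure.** 03 March to 12 March: 12 − 3 + 1 = 10 days, as SAP 6.3.3.9 states.

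**The two definitions applied.** Vaccination day is Day 1 (SAP 6.3.3.8), so vaccination date + 29 is Day 30. For an event present through Day 4 with no later entry:

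| Onset | Main (to Day 4) | Sensitivity (to Day 30) | Difference |
|---|---|---|---|
| Day 1 | 4 | 30 | 26 |
| Day 2 | 3 | 29 | 26 |
| Day 3 | 2 | 28 | 26 |
| Day 4 | 1 | 27 | 26 |

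In general the difference is 30 minus the last recorded symptom day. If a 'no' is entered on Day 5, the definitions agree (4 days for Day 1 onset). They are not strict bounds: an event with Day 1 onset recorded as present through Day 35 lasts 35 days under the main definition and 30 under the other.

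**Effect on the summary.** Let *f* be the share of a symptom's events with this pattern. The documents do not give it. The means differ by 26 × *f*:

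- *f* = 1%: 0.26 day
- *f* = 5%: 1.3 days
- *f* = 10%: 2.6 days
- *f* = 20%: 5.2 days

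Late 'no' entries add to this. From this pattern alone, one event puts the sensitivity maximum at 27 to 30 days, the upper quartile reaches that range only when *f* exceeds 25%, and the median only when *f* exceeds 50%.

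**What the planned tables reveal.** Dividing the observed gap between means by 26 gives the equivalent share of fully open Day 4 events: a gap of 1.3 days corresponds to 1.3 / 26 = 5%. This is approximate, because late 'no' entries and other last symptom days also contribute. The compliance tables cannot give the number of events, since they count diary days: 10 events missing 26 days and 26 events missing 10 days both give 260 missing days. Their denominator is also not spelled out for days without an entry.

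**Pooled groups.** Assume equal true durations and event rates in the two groups. The gap between definitions then differs between RSV-OA and RSV-A-AIR by 26 × *a* × (*f* alerts off − *f* alerts on), where *a* is the alerts-on share of RSV-A-AIR. With a 10-point difference in *f*:

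- 100 alerts-on participants: 26 × 100/1025 × 0.10 = 0.25 day
- 300: 26 × 300/1025 × 0.10 = 0.76 day
- 600 (all of Cohort 3, a ceiling): 26 × 600/1025 × 0.10 = 1.52 days

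**Where the mixing occurs.** The Part A Day 31 analysis contains only Cohorts 1 and 2, so RSV-A-AIR there is Cohort 1 alone. SAP 4.3.2.1 names alerts-on participants only within Cohort 3, which suggests that both Part A cohorts had alerts off. That comparison is then like for like. SAP 4.3.2.1 calls for both definitions without restricting them to one analysis step.

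**The case for a change.** The best case for a change is that the sponsor's sensitivity analysis shows that the result moves but not how many events move it. The remedy looks cheap: one count column and one split of existing tables, with no new data and both definitions kept. An alerts-off mean could be back-calculated from the two planned populations if event counts are shown, but a median or quartile could not. The Part A Day 31 analysis omits Cohort 3 participants enrolled before the alerts came on, and the SAP does not say outright that both definitions apply at that step.

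The factual part of this stands: the 26 days is exact, and no output counts the events ended at Day 30. It does not carry further, for three reasons.

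- Everything requested is additional reporting. No definition, population or estimate would be altered.
- The alerts-off split needs assumptions that the documents do not settle. Cohort 1 enrolment dates are not given. The alerts returned on a calendar date, so someone enrolled on 4 to 7 August reached Day 5 on 8 to 11 August and may have received them despite enrolling before the cut-off.
- The cohorts are not randomised and differ in age and disease (Protocol 4.1). A difference in mean duration between RSV-A-AIR and RSV-OA would be hard to attribute even with uniform alerts, and equal true durations are not a natural starting point.

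Redefining the compliance denominator so that every unclosed event is charged all days to Day 30 would not help. It adds 26 expected days per such event and lets a few of them dominate the percentage.

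**Conclusion.** No change to the plan is needed. This is a small gap in reporting that analysts can fill sensibly. The sponsor identified the alert failure, recorded it in the SAP version history, kept the main definition, added a declared sensitivity definition, and shows both alongside the subset with working alerts. The two definitions serve as approximate low and high readings for events with missing late entries, and the gap between them signals how far those entries matter.

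The size is 26 days per affected event and 0.26 day in the mean for each percentage point of such events; the actual share is unknown. The pooled-group effect of 0.25 to 1.52 days rests on an assumed 10-point difference in that share, on equal true durations and event rates, and on an unknown number of alerts-on participants. That Part A had alerts off throughout is inferred, not stated.

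Neither effect reaches a conclusion of the trial. Duration is not among the endpoints in SAP 1.1, its comparison between groups is not planned, and the non-inferiority analysis and the Day 1 to 4 occurrence percentages do not use it. A table footnote giving the number of events closed at Day 30 would be a courtesy to the reader. It can be added at reporting and does not require an amendment.
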